### Nursing Mothers

It is not known whether topically applied imiquimod is excreted in breast milk.

### Postmarketing experience

Individuals who used Imiquimod Cream after it was approved by the Food and Drug Administration have reported the following adverse reactions. It is not possible to reliably estimate their frequency or to establish a causal relationship to drug exposure. These events include the following:

- Angioedema - swelling, similar to hives, but the swelling is beneath the skin rather than on the surface
- Capillary leak syndrome - is a rare medical condition where the number and size of the pores in the capillaries are increased which leads to a leakage of fluid from them
- Cardiac Failure - the inability of the heart to fill with or eject blood due to any structural or functional cardiac conditions.
- Cardiomyopathy - serious disease in which the heart muscle becomes inflamed and doesn't work as well as it should.
- Arrhythmias - disorder of the heart rate (pulse) or heart rhythm, such as beating too fast (tachycardia), too slow (bradycardia), or irregularly.
- Chest pain - discomfort or pain in the chest that may be a key warning symptom of a heart attack
- Ischemia - a condition in which the blood flow (and thus oxygen) is restricted to a part of the body
- Myocardial infarction - commonly known as a heart attack, is the interruption of blood supply to a part of the heart
- Syncope - temporary loss of consciousness and posture, described as "fainting" or "passing out."
- Thyroiditis - inflammation of the thyroid gland
- Decrease in white blood count
- Decrease in red blood count
- Decrease in platelet count
- Abnormal liver function
- Agitation - Emotional state of excitement or restlessness
- Cerebrovascular accident – this is also known as a “stroke,” which is the loss of brain function(s) due to disturbance in the blood supply to the brain
- Convulsions - when a person's body shakes rapidly and uncontrollably

**IRB  
PB**

**Amended: 3/5/14**

## Memorial Sloan-Kettering Cancer Center IRB Protocol

**IRB#: 07-029A(6)**

- Depression - mental disorder characterized by an low mood accompanied by low self-esteem, and by loss of interest or pleasure in normally enjoyable activities
- Insomnia – when a person is unable to fall asleep or remain asleep for an adequate length of time
- Multiple Sclerosis aggravation – worsening of the symptoms of Multiple Sclerosis
- Paresis - partial loss of movement, or impaired movement
- Suicide - the act of a human being intentionally causing his or her own death
- Dyspnea - difficulty in breathing
- Proteinuria - the presence of an excess of proteins in the urine
- Exfoliative dermatitis - widespread scaling of the skin, often with itching, skin redness, and hair loss

### 12.0 CRITERIA FOR THERAPEUTIC RESPONSE/OUTCOME ASSESSMENT

The biopsied lesion will be the focus of the histologic assessment. All biopsies will be routinely sectioned and stained (H&E). Photographs will be obtained by the treating physician. Standardized 1:1 fixed distance photography will be performed with a contact camera with a built in light source to ensure standardized images. Millimeter scales will be included in each image to ensure spacial standardization.

Clinical response will be assessed by comparison of pairs of clinical photographs obtained at study completion and baseline. Pairs of photographs will be graded as:

- Complete response = reversion to clinically normal appearing skin.
- Partial response = 50% or greater reduction in diameter of affected skin.
- Progression = 50% or greater increase in diameter of affected skin.

Primary histologic evaluation will entail quantification of the number of involved areas /mm^2 that have Paget's cells. Histologic response will be graded as:

- Complete response = No evidence of Paget's cells
- Partial response = ratio of involved areas/mm^2 in post-treatment biopsy specimen/ pre-treatment biopsy specimen < 50%
- Progression = ratio of involved areas/mm^2 in post-treatment biopsy specimen/ pre-treatment biopsy specimen > 150%

We recognize the subjective nature of determining "significant" changes in appearance of the skin lesion. This problem, common to many dermatology studies, has defied a standardized technologic solution to date. We will use the method that is similar to that employed by a recently published study evaluating the effects of imiquimod on dysplastic nevi.xx In this study, Junctional lesional cells were counted in multiple high power fields and reported as lesional cells/mm^2 and lesional cell

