## Memorial Sloan-Kettering Cancer Center IRB Protocol

**IRB#: 07-029A(6)**

### 1.0 PROTOCOL SUMMARY AND/OR SCHEMA

Study Population	Patients with Recurrent Extramammary Paget's Disease (EMPD)
Study Design	Pilot, prospective cohort study
Therapy	Imiquimod 5% Cream applied T.I.W.
Duration of Therapy	12 weeks
Assessment of Response	a. Clinical assessment of before and after photographs by an independent reviewer b. Non-blinded histologic assessment of baseline biopsies and post therapy excisional biopsies 4 weeks after end of treatment
Number of evaluable subjects required	20
Target sample size	Assuming a 15% dropout rate, target sample size is 17

This is a pilot study of the use of a topical immunomodulatory agent, imiquimod, for the treatment of recurrent Extramammary Paget's disease (EMPD). In this protocol we will assess the clinical and histologic effects of topical imiquimod on recurrent EMPD.

Imiquimod 5% cream (Aldara, 3M Pharmaceuticals, St Paul, Minnesota) is an FDA approved safe and effective treatment of anogenital warts, superficial basal cell carcinoma, and actinic keratoses.i

Imiquimod has been demonstrated to induce cytokines that promote a TH1 immune response following both systemic and topical administration.ii The induced cytokines include alpha interferon, gamma interferon, and interleukin 12. The specific mechanism of action by which imiquimod eliminates warts, basal cell carcinoma, and actinic skin cancers is unknown.

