## Memorial Sloan-Kettering Cancer Center IRB Protocol

IRB#: 07-029A(6)

lesion is present or the patient refuses surgical excision at week 16, the patient will return for follow-up exams every 3 months for at least 2 years. The treating physician will continue to offer surgical excision at any later point during follow-up if the lesion is still present.

We will evaluate the clinical and histologic response of recurrent EMPD to treatment. Clinical response will be assessed by a pathologist (non-blinded) and an independent reviewer who will compare clinical photographs obtained at study completion to those obtained at baseline. Lesions will be evaluated based on size as having undergone complete response, partial response, no change, or progression. Histologic evaluation will entail quantifying the number of residual Paget cells following treatment. Side effects and toxicities of therapy will be monitored and recorded.

Presented below is the treatment schema for this prospective cohort.

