### 10.0 EVALUATION DURING TREATMENT/INTERVENTION

The patient will be seen in clinic at approximately six week intervals during treatment for examination (e.g. week 6 visit will be completed between 35-49 days, week 12 visit between 77-91 days, and week 16 visit between 105-119 days after baseline). Punch biopsy and photography will be performed at the baseline and 12 week visit. The lesion will be assessed after the initial 12 weeks of therapy by visual inspection by the treating physician. Photodocumentation of the area will also be performed at this time. If the lesion is still present, repeat punch biopsy with histologic assessment will be performed (week 12). If the lesion is still present after the initial 12 weeks of therapy, the treating physician will recommend excision of the lesion four weeks following completion of therapy (week 16) to permit resolution of treatment associated inflammation. During this four week time period, the patient will not use imiquimod 5% cream. Any lesion progressing to a clinical appearance suspicious for evolving adenocarcinoma will be excised prior to study completion. The patient will have a follow-up exam 6 weeks after excision and then every 3 months for at least 2 years. If no lesion is present or the patient refuses surgical excision at week 16, the patient will return for follow-up exams every 3 months for at least 2 years. The treating physician will continue to offer surgical excision at any later point during follow-up if the lesion is still present.

**IRB  
PB**

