**Amended: 3/5/14**

## Memorial Sloan-Kettering Cancer Center IRB Protocol

IRB#: 07-029A(6)

	Baseline	Week 6	Week 12	Week 16	Week 22 (if lesion was excised)	Every 3 months for 2 years
Clinical Assessment	✓	✓	✓	✓	✓	✓
Photography	✓		✓			
Biopsy	Punch biopsy of lesion		Repeat Punch biopsy of lesion	Excision of lesion if still present (recommended)		

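### The histologic outcome has two counting units and conflicting post-treatment specimens, so whether a patient is graded may depend on clinical response

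*Combined protocol and SAP*

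**What the plan says.** Section 2.0 has a single objective, covering clinical and histologic effects, so histology is half of it.

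**Unit.** The Section 1.0 narrative says: "Histologic evaluation will entail quantifying the number of residual Paget cells following treatment". Section 12.0, which holds the only grading rule, says: "Primary histologic evaluation will entail quantification of the number of involved areas", per mm², that contain Paget's cells. Partial response is a post-to-pre ratio of that count below 50%, progression a ratio above 150%, and complete response the absence of Paget's cells. Section 12.0 also likens its method to a published nevus study that counted lesional cells per mm².

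**Specimen.**
- Section 1.0, summary table: "Non-blinded histologic assessment of baseline biopsies and post therapy excisional biopsies 4 weeks after end of treatment".
- Section 1.0 narrative and Sections 4.1, 4.2 and 9.0: a punch at baseline and at week 12, with no condition.
- Section 10.0, schedule table: at week 12, "Repeat Punch biopsy of lesion", with no condition shown; at week 16, "Excision of lesion if still present (recommended".
- Section 10.0, text: first "Punch biopsy and photography will be performed at the baseline and 12 week visit", then "If the lesion is still present, repeat punch biopsy with histologic assessment will be performed (week 12".
- Section 10.0 also foresees patients without an excision: "If no lesion is present or the patient refuses surgical excision at week 16", they go on to follow-up visits.
- Section 12.0 refers only to a biopsy specimen taken after treatment, and names neither type nor week.

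No section says how histology is graded when the intended specimen is absent.

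**The concern.** Two people following this protocol could count different things in different tissue and report different histologic results for the same patients.

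The specimen conflict matters more. Excision is offered only for a persisting lesion and may be declined. The conditional sentence in Section 10.0 ties the week-12 punch to a persisting lesion as well. If either wording decides what is graded, patients who clear clinically get no histologic grade. Missing grades then depend on the other half of the objective, and a rate among graded patients may not represent the cohort.

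The unit conflict is narrower. It can move a patient into or out of partial response or progression. It cannot change complete response, because absence of Paget's cells is the same finding under either count.

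**Working it through.** **Inputs.** Section 14.0 gives 20 accrued, 15% dropout, 17 remaining, and a 95% interval of ±24%. (The Section 1.0 table attaches the word evaluable to 20; the Section 14.0 reading is used here.) The number of ungraded patients, m, is not in the documents, so a range is assumed.

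**Step 1: the plan's own figure.** 20 × (1 − 0.15) = 17. The worst-case half-width is 1.96 × √(0.5 × 0.5 / 17) = 0.238, or ±24%. It reproduces. It applies to a histologic rate only if all 17 patients have a grade.

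**Step 2: who has a specimen under each wording.**

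| Governing wording | Cleared patients | Lesion persists, excision refused |
|---|---|---|
| Section 1.0 table (excision) | no excision specimen | no excision specimen, but a week-12 punch exists |
| Section 10.0, conditional punch | no post-treatment punch | week-12 punch |
| Unconditional punch, done in everyone | week-12 punch | week-12 punch |

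Only the third row gives m = 0.

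**Step 3: size for complete response.** Let x be the number of histologic complete responses among the 17 − m graded patients. Over all 17, the rate lies between x/17 (every ungraded patient counted as no) and (x + m)/17 (every one counted as yes). The width is m/17 whatever x is.

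| Assumed m | Width m/17 |
|---|---|
| 3 | 17.6 points |
| 5 | 29.4 points |
| 9 | 52.9 points |

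Example with m = 9 and x = 1: among graded patients 1/8 = 12.5%; over all 17, from 1/17 = 5.9% to 10/17 = 58.8%. These bounds are before any sampling error.

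**Step 4: unit.** As an invented illustration, suppose treatment removes 75% of the cells in every involved area but the number of areas is unchanged. The area ratio is 1.0, which is neither partial response nor progression. The cell ratio is 0.25, which would be partial response if the same 50% cut-off were applied to cells.

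**The case against.** The strongest reply is that most of the text describes an unconditional week-12 punch, and the Section 1.0 table neither says that only excisions count nor cancels that punch. This stands. A reader might infer that patients who clear or refuse surgery have no post-treatment tissue at all. The documents do not support that. Refusers with a persisting lesion have a week-12 punch under both sentences of Section 10.0. Cleared patients lack one only if the single conditional sentence overrides the rest. Lacking the named specimen is not the same as lacking tissue.

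A reader might also infer that the rate among graded patients is certainly too low. That needs cleared patients to be histologically clear more often than the others. This is plausible, but it is not stated, and on the excision reading the ungraded also include refusers, for whom the direction is unknown. The bounds in Step 3 do not need the assumption.

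Two sources that might show the intent were not available: the case report form directions mentioned in Section 16.1.0 and the treatment schema, whose figure is not shown. Either might supply a counting rule or the biopsy path, but the conflicting sentences would still need reconciling.

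Finally, non-blinded histology is openly declared in Sections 1.0 and 14.0. It is a disclosed choice rather than a contradiction, so masking the count is a secondary improvement only.

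**Conclusion.** The point holds as a conflict of definition in the current text. The unit differs between Sections 1.0 and 12.0 and can affect partial response and progression. The graded specimen differs between the Section 1.0 table and the later sections, the week-12 punch is stated two ways within Section 10.0, and Section 12.0 resolves neither.

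The consequence depends on which wording governs. If it is excision or the conditional punch, histologic complete response over 17 patients is uncertain by the m/17 shown above, with m assumed. If the unconditional punch governs and is done in everyone, this loss does not arise. A reader might take this as a fault in the sample size. It is not: 17 patients and ±24% are correct as stated.

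This should be corrected, with medium confidence, because the unavailable sources may clarify the intent.

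**What to change.** 1. Reconcile Sections 1.0 (table and narrative), 4.1, 4.2, 9.0 and 10.0 (text and schedule) on which post-treatment specimen Section 12.0 grades, and on whether the week-12 punch is conditional. The sponsor decides both.
2. Use one unit throughout. The simplest route is to align the Section 1.0 narrative with Section 12.0's involved areas per mm² and its existing cut-offs, and to state one counting area used at both visits.
3. Compute the ratio only between specimens of the same type. Report any other histology separately, as Paget's cells present or absent.
4. Report how many patients are ungraded, by clinical response and reason (cleared, refused, other). Give histologic complete response among graded patients and over all evaluable patients, with bounds counting every ungraded patient first as no and then as yes.
5. As a secondary step, have the existing site pathologist do the response count on coded slides without visit labels.

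The cost is a wording amendment, a few extra lines in the report, and some coding and counting time. No extra biopsy, reader or patient is asked for. There are two downsides. Item 3 may leave fewer patients with a ratio; if excision is the specimen chosen, it has no like-for-like partner in a baseline punch. And treatment-associated inflammation may still reveal the visit on a coded slide.

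### Histologic partial response and progression rest on an undefined count of involved areas per mm², which, read as separate foci, need not fall as disease burden falls

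*Combined protocol and SAP*

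**What the plan says.** Section 12.0 states: "Primary histologic evaluation will entail quantification of the number of involved areas" per mm² that contain Paget's cells. Three histologic grades follow:

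- Complete response does not use the count: "Complete response = No evidence of Paget's cells".
- Partial response is a ratio of involved areas per mm², post over pre, with the limit written as "pre-treatment biopsy specimen < 50"%.
- Progression uses the same ratio, with the limit written as "pre-treatment biopsy specimen > 150"%.

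Both limits are strict. Section 12.0 does not say what counts as one involved area. It gives no rule for confluent disease, for low baseline counts, or for specimens of different size.

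Two other statements point to a different unit. The text of Section 1.0 says: "Histologic evaluation will entail quantifying the number of residual Paget cells following treatment". The dysplastic nevus study that Section 12.0 takes as its model worked on cells: "Junctional lesional cells were counted in multiple high power fields and reported as lesional cells/mm"².

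The post-treatment specimen also varies. The Section 1.0 summary table compares baseline biopsies with excisional biopsies taken four weeks after treatment ends. Sections 4.1, 4.2, 9.0 and 10.0 describe a punch biopsy at baseline and again at week 12.

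**The concern.** A count of areas carries no information on how much epithelium each area covers. If treatment clears the middle of a confluent lesion and leaves islands, the burden falls while the count rises. If baseline shows only one or two areas, the count is too coarse to register a partial reduction. Dividing by mm² does not repair this. It adds a dependence on how much tissue was examined, because a single confluent focus counts as one in a small specimen and one in a large specimen.

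Histologic effect is half of the only objective (Section 2.0), and Section 14.0 plans a response rate on 17 patients. A grade that can move against the disease would distort that description, and a confidence interval does not cover this kind of error. The point stands apart from the conflict between cells and areas. If the sponsor settled that conflict by keeping Section 12.0 and reading areas as foci, the grades would still misbehave.

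**Working it through.** **The plan's own figure.** Section 14.0 gives a 95% confidence interval of ±24% on 17 patients. It reproduces: 20 × 0.85 = 17, and 1.96 × √(0.5 × 0.5 / 17) = 0.238. The point below neither uses nor changes it.

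**Inputs.** From Section 12.0: the ratio of involved areas per mm², partial response below 50%, progression above 150%, complete response if no Paget's cells. Assumed: an area means one contiguous focus. Also assumed, because the documents give no values: the counts and the ratio of tissue areas.

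**Formula.** Let b and a be the baseline and post-treatment counts, and k the post/pre ratio of tissue area examined. Then R = (a/b)/k.

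**Equal tissue (k = 1).** Partial response needs a ≥ 1 and a/b < 0.5, so b > 2a ≥ 2. Hence b must be at least 3.

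| Baseline areas | 1 residual | 2 residual | 3 residual | 4 residual | 5 residual |
|---|---|---|---|---|---|
| 1 | 100%, neither | 200%, progression | 300%, progression | 400%, progression | 500%, progression |
| 2 | 50%, neither | 100%, neither | 150%, neither | 200%, progression | 250%, progression |
| 3 | 33%, partial response | 67%, neither | 100%, neither | 133%, neither | 167%, progression |

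From two baseline areas, a rise to three is exactly 150% and is not progression.

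**Count against extent (k = 1).** Illustration, with assumed sizes: one confluent area covering 100% of the epithelium is reduced to m foci of 10% each.

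| m | Extent ratio (m × 10% / 100%) | Count ratio (m / 1) | Grade by count |
|---|---|---|---|
| 1 | 10% | 100% | neither |
| 2 | 20% | 200% | progression |
| 3 | 30% | 300% | progression |
| 4 | 40% | 400% | progression |

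Every row would be a partial response if the same 50% limit were applied to extent.

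**Unequal tissue.**

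| k | 1 to 1 area (100%/k) | 2 to 1 areas (50%/k) | 1 to 2 areas (200%/k) |
|---|---|---|---|
| 0.6 | 167%, progression | 83%, neither | 333%, progression |
| 1.25 | 80%, neither | 40%, partial response | 160%, progression |
| 1.5 | 67%, neither | 33%, partial response | 133%, neither |
| 3 | 33%, partial response | 17%, partial response | 67%, neither |

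An unchanged single area is graded partial response for any k above 2. Two areas becoming one is graded partial response for any k above 1. The grade can therefore change with specimen size alone.

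**The case against.** The strongest objection is that the flaw depends on one reading of an undefined term. If an involved area means an involved microscopic field, confluent disease scores high at baseline and clearing lowers the count, so neither failure arises. Section 1.0 and the nevus study both speak of cells, which also avoids the problem. This stands as a limit on the claim: the documents show an undefined measure more firmly than a wrong one. It does not remove the need for a change. The literal wording allows the failing reading, and the sentence adopting a method similar to the nevus study follows remarks on skin appearance, so it does not settle the histologic unit.

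A reader might infer more than the documents support:

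- *The count never falls as disease falls.* It does fall when whole foci clear; the defensible statement is that it need not fall.
- *Partial response is impossible from one or two areas, and fragmentation is always progression.* Both hold only with equal tissue examined and areas read as contiguous foci. At k = 1.5, one area becoming two is not progression.
- *A share of patients misgraded can be stated.* The documents give no baseline counts or patterns. A 3 mm punch at the lesion edge makes low counts plausible, but any percentage would follow from an assumed baseline pattern and mode of clearing. A lesion that shrinks from its edge stays one area and is never graded progression when equal tissue is examined.
- *A false progression grade is a safety signal.* Removal from study for progression under Section 13.0 rests on worrisome clinical change with histology showing invasive carcinoma, not on the 150% limit.

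Two further points stand. This is a descriptive pilot, and clinical response is graded separately on diameter.

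**Conclusion.** The point holds in a limited form and should be corrected. As written, the histologic measure is undefined. Read as a count of separate foci, it can grade a shrinking lesion as progression and, with equal tissue, cannot register partial response from fewer than three baseline areas. With unequal tissue, it can grade an unchanged single area as either partial response or progression.

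The direction of the overall error is not fixed. Equal specimens push towards too few partial responses; a larger post-treatment specimen pushes the other way. Each misgraded patient moves a 17-patient rate by 1/17 = 5.9 percentage points, but only if partial response counts as response, which Section 14.0 does not say. Complete response is unaffected. How many patients would be misgraded cannot be computed from the documents.

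**What to change.** In Section 12.0, grade partial response and progression on a measure of burden read from the same H&E slides. Two would serve:

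- Paget cells per mm², the unit that Section 1.0 and the cited nevus method indicate, with the tissue area or fields to be counted stated; or
- involved epithelial length divided by total epithelial length.

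Choose one. Keep the limits of <50% and >150%, keep complete response as no Paget's cells, and report the number of foci only as a description. Reconcile the unit in the Section 1.0 text with Section 12.0, and reconcile the post-treatment specimen in the Section 1.0 summary table with Sections 4.1, 4.2, 9.0 and 10.0.

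The cost is a short edit to Section 12.0 with matching wording in Section 1.0, one case report form field, and a little more reading time for the same pathologist. Retained slides could be re-read. Treatment and sample size do not change. One limit remains: either measure still depends on where the punch is taken, because the biopsy sits at the lesion edge and is meant to include some normal tissue.
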